#### 4.6 LOST TO FOLLOW-UP

Subjects who miss at least two consecutive visits, as defined by the visit windows and cannot be contacted, may be considered lost to follow-up. All follow-up attempts will be documented and kept with the subject's source documentation, and the applicable CRFs will be completed.

Subjects that voluntarily withdraw consent after implantation with the HMIOL will be considered Lost to Follow-Up.

#### 4.7 STUDY COMPLETION

ClarVista will notify the Investigators when to contact the IRB / EC to announce study completion at the site.

#### 4.7.1 EARLY STUDY TERMINATION

ClarVista has the right to terminate this study at any time. Reasons for terminating the study may include, but are not limited to, the following:

- The incidence or severity of adverse events in this or any ongoing studies involving the same technology (if applicable), indicates a potential health hazard to subjects
- Subject enrollment is unsatisfactory
- Data recording is inaccurate or incomplete.

In the event of premature study termination, appropriate notification will be given to the Investigators, IRB / ECs, and regulatory bodies as applicable. In addition, ClarVista (or designee) will instruct all Investigators to discontinue dispensing study materials or treatments, will ensure all subjects complete appropriate follow-up, and will arrange study closeout visits at each site as appropriate.

#### 4.8 Transportation and Meal Allowance

Subjects will receive monetary allowance to cover transportation and meal expenses as specified in the ICF.

Rev.03, 7 January 2016 Confidential Page 19 of 32

**Document:** TDOC-0056124 **Version:** 1.0; CURRENT; Most-Recent; Effective

Status: Effective

CLARVISTA MEDICAL PROTOCOL CVM-00001 Rev.03

#### 4.9 CONCOMITANT THERAPIES

#### 4.9.1 CONCOMITANT MEDICATION

Concomitant medications are any prescription drugs used by a subject until conclusion of study participation. Any medication the Investigator deems in the best interest of the subject, is acceptable to prescribe or administer. However, any and all ophthalmic medications are to be recorded in both the Concomitant Medication source document and CRF as well as the reason for use (indication). An AE is to be reported and/or recorded as appropriate (see Section 6.0).

#### 4.9.2 CONCOMITANT PROCEDURES

A concomitant procedure is any invasive or non-invasive ocular or peri-ocular procedure that takes place during study participation and will be captured in both the Concomitant Procedure Source Document and CRF. The following are examples of two such procedures:

- Fellow Eye cataract extraction and IOL implantation, which will be listed as "Phaco with PCIOL."
- Neodymium: Yttrium-aluminum-garnet (Nd:YAG) procedure to treat Posterior Capsule Opacification (PCO), if necessary. This will be listed as "Nd:YAG Capsulotomy."

**Note:** Any Nd:YAG capsulotomy procedures prior to exit will be performed only in response to spontaneous subject complaints (i.e. not solicited by study personnel) of reduced Visual Acuity (VA) or glare that affects functional vision, which is associated with PCO or striae, and captured on the eCRF in SLE findings.

An AE is to be reported and/or recorded as appropriate (see Section 6.0). Any procedure reported in the Concomitant Procedure eCRF must have a corresponding Indication listed in either the Ocular History or AE CRF (Only exception: PCO – See Section 6.1 for further details).

#### 4.10 PROTOCOL DEVIATIONS

All protocol deviations, the date of deviation, and reason will be documented in the Source Document and eCRF. All deviations will be categorized as either major or minor in the following manner:

#### Major:

- Deviations impacting subject safety
- Deviations impacting subject rights
- Deviations impacting data integrity

#### Minor:

All other deviations (e.g. out of window visits, missed data point, etc.)

All major deviations must be reported by the Investigator to the Sponsor and IRB/EC immediately. Subject assessments will continue per protocol for the duration of planned participation unless the deviations put the subject at risk or the subject's condition requires that he/she be discontinued from the study.

Rev.03, 7 January 2016 Confidential Page 20 of 32

**Document:** TDOC-0056124 **Version:** 1.0; CURRENT; Most-Recent; Effective

Status: Effective

CLARVISTA MEDICAL PROTOCOL CVM-00001 Rev.03

### 5.0 STUDY MATERIALS

# 5.1 DESCRIPTION OF TEST ARTICLE

| The HARMONI™ Modular Intraocular    |                    | -      | investigational | device | designed | to allov | v safe |
|-------------------------------------|--------------------|--------|-----------------|--------|----------|----------|--------|
| exchange or adjustment of an IOL op | tic after implanta | ation. |                 |        |          |          |        |
|                                     |                    |        |                 |        |          |          |        |
|                                     |                    |        |                 |        |          |          |        |
|                                     |                    |        |                 |        |          |          |        |
|                                     |                    |        |                 |        |          |          |        |
|                                     |                    |        |                 |        |          |          |        |
|                                     |                    |        |                 |        |          |          |        |
|                                     |                    |        |                 |        |          |          |        |
|                                     |                    |        |                 |        |          |          |        |
|                                     |                    |        |                 |        |          |          |        |
|                                     |                    |        |                 |        |          |          |        |
|                                     |                    |        |                 |        |          |          |        |
|                                     |                    |        |                 |        |          |          |        |
|                                     |                    |        |                 |        |          |          |        |

FIGURE 3 - THE HARMONI™ MODULAR INTRAOCULAR LENS (HMIOL) SYSTEM

The HMIOL includes a base component (A) and an optic component (B) that are delivered and assembled (C) in the eye.

All components are sterilized using ethylene oxide (EtO) and has a

Effective Date: 24-Jun-2019

shelf life 1 year from the date of sterilization.

#### Test article:

- HARMONI™ Modular Intraocular Lens System Base Component
- HARMONI™ Modular Intraocular Lens System Optic Component

#### 5.1.1 Instructions for Use – Study Eye

Refer to the Surgical Guide for all use and administration details.

#### 5.2 PACKAGING AND LABELING

All packaging and labeling will be consistent with the current study design. The labeling will include at a minimum, the following:

- Sponsor name and address
- "For Single Use Only" statement (or equivalent symbol)
- Sterility symbol
- Storage temperature range requirements or equivalent
- Expiration date
- Power designation

Rev.03, 7 January 2016 Confidential Page 21 of 32

**Document:** TDOC-0056124 **Version:** 1.0; CURRENT; Most-Recent; Effective

Status: Effective

CLARVISTA MEDICAL PROTOCOL CVM-00001 Rev.03

Unique serial number

Model number

#### 5.3 ACCOUNTABILITY

The Investigator is responsible for keeping accurate accountability records of the number of study lenses received, dispensed, and returned to Sponsor. The study lenses must be stored under the appropriate conditions in a secure area and are to be implanted only in subjects enrolled in the study, in accordance with the conditions specified in this protocol.

All accountability records will include the following:

- Model and serial numbers
- · Receipt date
- · Quantities received
- Initials (attributability) of site personnel who received, dispensed, or returned study lenses
- Date of use
- Subject treated with the study lens (by Subject ID and Initials only)
- Date returned to Sponsor
- Defective or damaged study devices

Periodically throughout the study and/or upon completion, the Sponsor (or designee) will review and verify the Investigator's accountability records. Following verification, and as directed by the Sponsor, all unused and explanted products must be returned to the Sponsor.

**Note:** In addition, any study lenses or components deemed defective, damaged, malfunctioning, or explanted must be retained by the site and returned to the Sponsor for evaluation. Under no circumstances are any components to be discarded or otherwise disposed of. If there is any question as to the applicability of this directive, consult the Protocol Contacts page of this protocol and discuss the situation with a Sponsor representative.

#### 5.4 OTHER MATERIALS

Additional materials can be provided to sites for the duration of the study on an as-needed basis and may include:

- Medicel injectors
- IOL micro-incision cutter and forceps

#### 6.0 Adverse Events

Safety assessments include ocular adverse events, all serious adverse events, and adverse device events. The reporting time period is from the time of consent through the last study visit (1 Month Visit post-primary cataract extraction for Cohort 1 and post-optic exchange for Cohort 2).

#### 6.1 Definitions

6.1.1 Adverse Event (AE)

Rev.03, 7 January 2016 Confidential Page 22 of 32

**Document:** TDOC-0056124 **Version:** 1.0; CURRENT; Most-Recent; Effective

Status: Effective

CLARVISTA MEDICAL PROTOCOL CVM-00001 REV.03

An AE is any untoward ocular event in a subject that does not necessarily have a causal relationship to the study device or protocol. AEs include Adverse Device Effects (ADEs). Conditions or diseases that are chronic but stable should not be recorded on AE pages of the CRF. Similarly, changes in a chronic condition of disease that are consistent with natural disease progression are NOT adverse events and also should not be recorded on the AE pages of the CRF.

Refer to Section 6.3.1 for instructions regarding events that require expedited reporting to the Sponsor and IRB/EC.

Experience with cataract surgery and the implantation of IOLs has shown that some conditions can be considered normal or expected events following these procedures. The following may be considered normal or expected events after cataract surgery and only need to be reported as AEs as specified here:

- Iritis (cell / flare) if treated
- Persistent Corneal Stroma Edema (if present at 1 Month)
- Increased IOP only if medical/surgical intervention is required (i.e. medication, paracentesis manipulation)
- VA decrease of 10 or more letters (2 lines) from any previous visit not secondary to any underlying condition
- Any expected post-operative ocular event requiring a change in standard postoperative medication regimen

Note: PCO is not to be reported as an AE, as per ISO 11979-7:2014.

Particular attention should be paid to ensure timely and accurate reporting of any of the following cataract surgery related events:

- Endophthalmitis
- Capsular injury
- Vitreous loss
- Macular edema
- Retinal detachment
- Lens dislocation
- Moderate to severe corneal edema
- Pupillary block / angle closure
- Hypopyon or hyphema

#### 6.1.2 Adverse Device Effect (ADE)

An ADE is any untoward or unintended effect, event, or response surrounding and with a causal relationship with the use of a medical device. This definition may include any event resulting from insufficiencies or inadequacies in the instructions for use or the deployment of the device or other device malfunctions. This definition includes any event that is a result of a user error and any event that affects a user of the device (i.e. caregiver, bystander, etc).

Rev.03, 7 January 2016 Confidential Page 23 of 32

**Document:** TDOC-0056124 **Version:** 1.0; CURRENT; Most-Recent; Effective

Status: Effective

CLARVISTA MEDICAL PROTOCOL CVM-00001 REV.03

#### 6.1.3 UNANTICIPATED ADVERSE DEVICE EFFECT (UADE)

A UADE is any ADE, which is unanticipated and poses a risk to health or safety, or any life-threatening problem or death caused by or associated with a device, if that effect, problem, or death was not previously identified in nature, severity or degree of incidence (see Investigator Brochure [IB]). UADEs also include any unanticipated sight-threatening events and any other unanticipated serious problem associated with a device that relates to the rights, safety, or welfare of subjects.

#### 6.1.4 DEVICE DEFICIENCIES (DD)

A Device Deficiency (DD) is a failure of the device to meet its performance specifications or expectations, or otherwise not perform as intended. This can include either a malfunction or damage to the device or any part thereof, regardless of the source of malfunction or damage, including user error, and regardless of the presence of injury (or lack thereof) to subject, user, or bystander.

#### 6.2 AE EVALUATION

AEs experienced in this study may be associated with the study device (i.e. ADE) or the study protocol as demonstrated in the following non-exhaustive list of examples:

#### Study Device (ADE)

- · IOL dislocation
- Explant due to haptic break/damage
- Explant due to base and/or optic damage

#### **Study Protocol**

- Allergic reaction to dilating drops
- Lens remnants following surgery
- Capsular tear during surgery to implant study device

#### 6.2.1 EVALUATION

All AEs will be evaluated for and by the following criteria:

- Classification (SAE, AE, ADE or combination)
- Diagnosis (or description if ADE)
- Severity
- · Relationship (Causality) to study protocol or device
- Outcome
- Treatment or action taken

#### 6.2.1.1 CLASSIFICATION

When evaluating AEs, the Investigator must determine if the event is serious using the following guidelines:

A Serious Adverse Event (SAE) is any AE (ocular or non-ocular) that:

· results in death

Rev.03, 7 January 2016 Confidential Page 24 of 32

**Document:** TDOC-0056124 **Version:** 1.0; CURRENT; Most-Recent; Effective

Status: Effective

CLARVISTA MEDICAL PROTOCOL CVM-00001 REV.03

- results in serious injury, defined as:
  - ♦ life-threatening
  - permanent impairment of a body function (e.g. blindness) or structure
  - necessitates medical or surgical intervention to prevent permanent impairment of a body function or permanent damage to a body structure, or
  - ◆ results in a potentially sight-threatening condition
- · is a malfunction that might cause or contribute to a serious injury or death if it were to recur
- requires in-patient hospitalization or prolongation of existing hospitalization\*, or
- leads to fetal distress, fetal health, a congenital abnormality, or birth defect

\*Hospitalization is a criterion for assessment of seriousness. Hospitalization in the absence of a medical AE is not in itself an AE. For example, the following reports of hospitalization without a medical AE should not be considered either serious or an AE:

- admission for treatment of a pre-existing condition not associated with the development of a new AE or
  with worsening of the pre-existing condition (e.g. for work-up of persistent pretreatment lab abnormality)
- social admission (e.g. subject has no place to sleep)
- administrative admission (e.g. for yearly physical exam)
- optional admission not associated with a worsening of a pre-existing condition (e.g. elective cosmetic surgery or elective surgery for pre-existing repair of the Achilles tendon [which had not worsened while on study])
- hospitalization for admission without a medical AE

NOTE: For the purposes of this protocol, any UADE will be considered an SAE.

#### 6.2.1.2 DIAGNOSIS OR DESCRIPTION

In all instances, it is preferable to report all AEs and SAEs by diagnosis rather than a sign or symptom if possible. This may necessitate the revision of a previously reported AE or SAE as more information is obtained.

#### 6.2.1.3 SEVERITY

When evaluating AEs, the Investigator must determine the severity of symptoms using the following guidelines:

- Mild: Subject awareness of a sign or symptom that is easily tolerated, requires no treatment, and does not interfere with the subject's daily activities
- Moderate: Subject awareness of a sign or symptom which may be a low level of concern to the subject
  and may interfere with daily activities, but can be relieved by simple therapeutic care
- Severe: A sign or symptom that interrupts the subject's daily activity and requires systemic therapy or other treatment

6.2.1.4 RELATIONSHIP (CAUSALITY) TO STUDY DEVICE OR STUDY PROTOCOL

Rev.03, 7 January 2016 Confidential Page 25 of 32

**Document:** TDOC-0056124 **Version:** 1.0; CURRENT; Most-Recent; Effective

Status: Effective

CLARVISTA MEDICAL PROTOCOL CVM-00001 REV.03

When evaluating AEs, the Investigator must evaluate the relationship of the event to the study device and study protocol, using the following guidelines:

- Not Related: AEs which are clearly and incontrovertibly due to causes other than the study device or study protocol (e.g. concomitant disease, etc)
- Related: AEs which are felt with a reasonable degree of certainty to be related to the study device or study protocol
- Unknown: Adverse events for which a connection with the study device or study protocol cannot be ruledout with certainty, or not enough information is available to assess the relationship

#### 6.2.1.5 OUTCOME

The clinical outcome of an AE will be categorized as follows:

- · Resolved without sequellae
- Resolved with sequellae (specify)
- Ongoing (i.e. continuing at time of study discontinuation)
- Death

#### 6.2.1.6 TREATMENT OR ACTION TAKEN

Treatment or Action Taken will be categorized as follows:

- None
- Medical Intervention (specify on Concomitant Medication Source and CRF)
- Surgical Intervention (specify on Concomitant Procedure Source and CRF)
- Other (specify)

#### 6.3 REPORTING

#### 6.3.1 ON-SITE EXPEDITED REPORTING

The Investigator is obligated to report the following to the Sponsor within 24 hours of becoming aware of the event to ensure the safety of all participants in the study and to meet regulatory reporting requirements:

- All SAEs, regardless of relationship to study device or study protocol
- All AEs determined to be related to the study device (ADEs or UADEs)
- All HMIOL explants (consult Medical Monitor listed on Protocol Contacts page prior to explant, if possible)
- All Device Deficiencies (DD)

Refer to the Protocol Contacts page for appropriate Sponsor contact to report the above events.

NOTE: Any explanted HMIOL devices, exchanged HMIOL optics, or any components of the HMIOL System presenting a deficiency or malfunction are to be retained by the site until collected by the Sponsor. Under no circumstances are they to be destroyed or otherwise discarded.

Rev.03, 7 January 2016 Confidential Page 26 of 32

**Document:** TDOC-0056124 **Version:** 1.0; CURRENT; Most-Recent; Effective

Status: Effective

CLARVISTA MEDICAL PROTOCOL CVM-00001 Rev.03

When reporting these events to the Sponsor, the site should forward any supporting documents along with the appropriate reporting form and complete the corresponding CRF, if applicable. Sites must also report applicable events to the reviewing IRB/EC per its established reporting procedures.

#### 6.3.2 OFF-SITE SAE REPORTING

As a multicenter clinical trial, the Investigators may receive "off-site" reports (e.g. an SAE Report). These are Sponsor reports of SAEs which occurred at other sites for the same trial, or in different trials using the same test article, that met the criteria for reporting. These should be reported to the reviewing IRB per their established reporting procedures.

#### 6.3.3 Reporting of Complaints for Ancillary Marketed Products

Any complaints, malfunctions or similar events related to ancillary marketed products used in this study should be reported by the Investigators in accordance with the reference information provided on the associated commercial packaging.

#### 6.3.4 Adverse Events and Serious Adverse Events at Subject Exit

Ongoing SAEs and ADEs will be followed until resolution or no further change in the condition is expected. Non-serious AEs that are ongoing at study exit visit or upon discontinuation from the study will be followed per the Investigator's standard of care. Documentation in the CRF of this follow-up is not required although subject care should continue as appropriate.

#### 6.4 SAFETY MONITORING AND REVIEW

All reported AEs will be reviewed on a weekly basis and assessed for trending and causality to study device or procedure. ADEs, UADEs, DDs, and SAEs will be reviewed upon receipt of expedited reporting (Section 6.3.1). Any unexpected trends or events will necessitate careful review and assessment of any change in the risks associated with participation or study continuation.

If an event occurs affecting a subject's risk of participation, Off-Site Reporting (Section 6.3.2) will be utilized to update sites and the IRB(s) / EC(s). If the safety profile of the event provides for the continuation of the study, Informed Consent Forms will be revised as necessary to ensure subjects' consent to continue participation given the known revised risks.

As outlined in Section 4.7.1, the Sponsor reserves the right to discontinue enrollment at any time.

#### 7.0 CLINICAL ENDPOINTS

# 7.1 ENDPOINTS

Safety will be evaluated by assessing the following:

HMIOL Cohort 1

- UCDVA by study visit
- MR by study visit

Rev.03, 7 January 2016 Confidential Page 27 of 32

**Document:** TDOC-0056124 **Version:** 1.0; CURRENT; Most-Recent; Effective

Status: Effective

CLARVISTA MEDICAL PROTOCOL CVM-00001 REV.03

- BCDVA by study visit
- Surgeon questionnaire
- AE incidence rate
- Device deficiencies
- SSI (planned Optic Exchanged procedures excluded)

#### **HMIOL Cohort 2**

- UCDVA by study visit
- MR by study visit
- BCDVA by study visit
- Surgeon questionnaire
- AE incidence rate
- · Device deficiencies
- SSI (planned Optic Exchanged procedures excluded)

#### 8.0 STATISTICAL METHODS

This is a study to evaluate visual and refractive outcomes of patients with HMIOL during primary cataract surgery and subjects with HMIOL optic exchange. In general, the analyses will be provided based on available data. The mean, standard deviation, minimum, and maximum will be prepared for the continuous clinical parameters, and counts and percentages will be presented for the categorical outcomes.

#### 8.1 SAMPLE SIZE CALCULATION

This study is not designed to power a hypothesis.

# 8.2 Analyses Populations

Subjects that are screened but disqualified based on the preoperative and intra-operative eligibility criteria will be excluded from the analyses. However, their reasons for the screen failure will be summarized. The analyses populations defined below are defined for the study lens.

#### 8.2.1 IMPLANTED-EYE POPULATION

The Implanted-Eye Population consists of eyes with successful HMIOL implantations during surgeries.

#### 8.2.2 PER PROTOCOL POPULATION

The **Per Protocol** (PP) Population contains eyes with successful HMIOL implantations during surgeries and do not have major protocol deviation (such as improperly enrolled in the study or lens power calculation errors) and will be considered the primary population for effectiveness outcomes.

The protocol deviations will be determined reviewed by ClarVista clinical personnel prior to analysis.

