5.6. Effectiveness Endpoints

Effectiveness endpoints will be summarized in the per-protocol population for each cohort at each study visit for which they are available. See Appendix A for a listing of scheduled assessments by visit.

Rev.02, 1 March 2018 Confidential Page 4 of 8

Document: TDOC-0056125 **Version:** 1.0; CURRENT; Most-Recent; Effective

Status: Effective

Protocol CVM-00001 Statistical Analysis Plan

ClarVista Medical, Inc.

Effective Date: 24-Jun-2019

6. Sample Size

The sample size for this study was not based on any statistical criteria. The sample size was chosen to provide sufficient experience and feedback regarding the ClarVista HARMONI™ Modular Intraocular Lens System at five investigative centers.

7. Analysis Populations

Safety Population: Eyes with attempted study lens (HMIOL) implantation, (successful or aborted after contact with the eye). The intraoperative and postoperative AEs and device deficiencies, slit lamp examination, dilated fundus examination, and IOP will be summarized based on the safety population.

Per-Protocol Population: Eyes with successful HMIOL implantation that do not have major protocol deviations (such as improperly enrolled in the study or lens power calculation errors). The effectiveness endpoints will be summarized based on the per-protocol population.

10. Interim Analyses

There are no plans for formal interim analyses for the purposes of study modification or possible early termination. Any interim analyses will be administrative in nature and results will not be distributed to Investigators or subjects to prevent bias from exposure to accruing study results.

Interim Safety Summary: Safety outcomes will be evaluated when all eyes in Cohort 1 and Cohort 2 have completed the 1 Month Visit following primary cataract extraction and optic exchange, respectively (post-optic exchange for Cohort 2).

Final Safety and Effectiveness outcomes will be evaluated when all study subjects complete the final visit or exit the study.

11. Deviations from the Statistical Analysis Plan

Any deviations from the Statistical Analysis Plan will be noted and described with appropriate statistical and clinical rationale as needed.

12. References

1. ISO 11979-7:2014 Ophthalmic implants — Intraocular lenses — Part 7: Clinical investigations.

Rev.02, 1 March 2018 Confidential Page 5 of 8

Document: TDOC-0056125 **Version:** 1.0; CURRENT; Most-Recent; Effective

Status: Effective

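### The plan does not require per-protocol exclusions, including those for lens power errors, to be settled without sight of post-operative refraction or acuity, and gives no uniform rule for finding such errors

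*Protocol*

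**What the plan says.** Protocol section 8.2.2 admits to the per-protocol set successfully implanted eyes that "do not have major protocol deviation (such as improperly enrolled in the study or lens power calculation errors"), and the set "will be considered the primary population for effectiveness outcomes". On who decides, it says: "The protocol deviations will be determined reviewed by ClarVista clinical personnel prior to analysis". SAP section 7 repeats the examples ("such as improperly enrolled in the study or lens power calculation errors") and summarises effectiveness in the per-protocol set, as does SAP section 5.6.

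Protocol section 4.10 defines a major deviation by its effect on safety, subject rights or data ("Deviations impacting data integrity"). Neither document defines a lens power calculation error or says how one is to be detected.

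Four other provisions bear on the point:

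- Recording (Protocol 4.10): "All protocol deviations, the date of deviation, and reason will be documented in the Source Document and eCRF".
- Reporting (Protocol 4.10): "All major deviations must be reported by the Investigator to the Sponsor and IRB/EC immediately".
- Protocol 9.1.1 promises masking as far as possible, in general terms.
- Protocol 8.3.1 has each endpoint analysed in the Implanted-Eye Population as well as the per-protocol set.

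SAP section 2 states that its analyses supersede those of the protocol. SAP section 7 defines only a Safety and a Per-Protocol population.

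**The concern.** Lens power selection acts directly on refraction and uncorrected acuity, both of which are endpoints here. A natural reason to reopen a power calculation is that the refraction missed its target. If that is how errors come to light, an eye with a poor result is examined and excluded, while an eye with the same error that landed near target is never looked at. Exclusion then depends on the outcome.

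A review held before analysis does not by itself prevent this, because outcome data may be visible long before analysis starts. Protocol 9.1.1 lets sponsor personnel review or collect completed case report forms at any time during the study. SAP section 10 withholds interim results from investigators and subjects but does not mention sponsor staff.

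The study is non-randomised and describes no concurrent control, so a selective loss of off-target eyes passes straight into the device estimate. The proportion near target would rise, and the spread of refractive error would tend to narrow. Cohort 2 is a subset, so each eye removed there counts for more.

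**Working it through.** **Plan's own figure.** There is none to reproduce. Protocol 8.1 and SAP section 6 state no powered hypothesis and no statistical basis for the sample size. What follows is illustration only.

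**Inputs**

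- Eyes: N = 200, assumed. The protocol synopsis gives up to 200 subjects, and some may receive the lens in both eyes.
- Starting rates: 45% within 0.5 D and 85% within 1 D. These are benchmarks for conventional surgery cited in Protocol section 1.0, not assumptions made for this device.
- Eyes removed, k: assumed. The plan gives no expected number.

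**Formula.** If all k removed eyes are off target, the rate after exclusion is successes / (N − k). If exclusion is unrelated to outcome, the expected rate does not change.

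**Within 0.5 D** (0.45 × 200 = 90 eyes on target)

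- k = 5: 90/195 = 46.2%
- k = 10: 90/190 = 47.4%
- k = 20: 90/180 = 50.0%

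**Partial selection.** Suppose 10 eyes are removed, 5 because of their outcome and 5 at random. The random removals leave the expected rate unchanged, so it is 90/(200 − 5) = 46.2%.

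**Within 1 D** (0.85 × 200 = 170 eyes), with every removed eye more than 1 D off

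- k = 10: 170/190 = 89.5%
- k = 20: 170/180 = 94.4%

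**Scale against sampling error.** The 95% half-width is 1.96 × √(p(1 − p)/N).

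- p = 0.45: 1.96 × √(0.45 × 0.55/200) = 6.9 points. The shifts of 1.2, 2.4 and 5.0 points are all smaller.
- p = 0.85: 1.96 × √(0.85 × 0.15/200) = 4.9 points. Removing 10 eyes shifts the rate by 4.5 points, about one half-width.

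With 400 eyes and the same fraction removed, the percentages do not change: 180/380 = 47.4%.

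**Does any existing provision close the gap?**

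| Provision | What it does | What it leaves open |
|---|---|---|
| Review before analysis (Protocol 8.2.2) | Fixes when deviations are settled | What the reviewers have seen by then |
| Dated record and immediate reporting (Protocol 4.10) | Leaves a trail at the site | An error noticed only because the refraction was poor |
| General masking (Protocol 9.1.1) | States an intention | Not tied to the deviation review |
| Implanted-Eye analysis (Protocol 8.3.1) | Would expose selective removal | Leaves the primary result as it is, and does not appear in the SAP text available |

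**The case against.** The strongest reply is that the documents are silent on masking at this step, and silence is not evidence of unmasked review. That is right. A reader might infer that sponsor staff decide with the refractive results in front of them, or that poor eyes will be taken out. The documents support neither inference. They do not say what the deviation reviewers see, and Protocol 9.1.1 states a general intention to mask.

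The wording on who decides is also garbled. It may mean that the sponsor originates the deviations, or only that it reviews those the sites have recorded. Site recording and immediate reporting are real safeguards, and the Implanted-Eye analysis would reveal a discrepancy wherever it is carried out.

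A reader might further conclude that the SAP has no other effectiveness analysis. That cannot be confirmed. Its contents list names sections 8 (sensitivity) and 9 (subgroups), whose text is not in the copy available.

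The numbers are open to challenge too. The exclusion counts are invented for illustration, selection is taken as complete, and the proportion within 0.5 D is not a listed endpoint, although SAP 5.1 allows continuous measures to be categorised. The study is descriptive, and the SAP calls it a feasibility study.

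These points limit what can be claimed and how serious it is. None of them supplies a rule for deciding the per-protocol list independently of outcome.

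**Conclusion.** The point holds as a gap in the plan. Nothing requires per-protocol exclusions to be settled without sight of post-operative refraction or acuity, and nothing sets a uniform way to detect a lens power error. Outcome-prompted exclusion from the primary effectiveness set is therefore permitted, and in the SAP text available that set is the only one used for effectiveness.

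On the illustrative inputs, the effect on the within-0.5 D rate runs from about 1 to 5 points for 5 to 20 eyes removed, and is smaller if selection is partial. This rests on the assumed number of eyes, the borrowed benchmark and the assumed exclusions. The mechanism is plausible but not documented. With no powered hypothesis, the consequence is a biased estimate, not a false-positive conclusion. The change should be made because it is cheap and reduces the bias itself.

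**What to change.** 1. Define a lens power calculation error from pre-operative biometry and calculation records alone.
2. Apply that check to every implanted eye, whatever its refraction. This is the main protection: a restricted listing cannot mask staff who have already seen outcomes, whereas a fixed rule applied to all eyes leaves little room for selection.
3. Finalise, sign and date the per-protocol list before database lock, from a listing that omits post-operative acuity and refraction.
4. Carry the Implanted-Eye effectiveness summary of Protocol 8.3.1 into the SAP, and list each excluded eye with its reason.

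The cost is modest: extra checking of existing records by existing staff, one restricted listing and one additional set of summary tables. No new visits or measurements are needed.
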